7.1.1 Confidentiality of Subject Records

By signing the protocol, the Investigator agrees that the NIH/NHLBI or IRB representative may consult and/or copy study documents in order to verify CRF data. By signing the consent form, the subject agrees to this process. If study documents will be photocopied during the process of verifying CRF information, the subject will be identified by unique code only and full names and similar identifying information (such as medical record number or social security number) will be masked.

The Clinical Site Investigators will ensure that the identity of subjects will be protected. All study records will be maintained in a secure fashion with access limited to essential study personnel only. All study documents submitted to the Coordinating Center will have identifiers removed other than dates of birth and service and subjects will be identified with a study-specific identification number only. The Clinical Site Investigators will maintain, in a secure location, an enrollment log that includes subject identifying information and links subjects to their study-specific identification number.

7.2 Data Capture

7.2.1 Source Documents

All source data will be kept and merged and/or entered into the electronic clinical trial software (REDCap). Source data is all information, original records of clinical findings, observations, or other activities in a clinical trial necessary for the reconstruction and evaluation of the trial. Source data are contained in source documents. Examples of these original documents and data records include: hospital records, clinical and office charts, laboratory notes, memoranda, subjects' diaries or evaluation checklists, recorded data from automated instruments, copies or transcriptions certified after verification as being accurate and complete, subject files, and records kept at the pharmacy, at the laboratories, and at medico-technical departments involved in the clinical trial.

Data will be collected at both study sites during the Screening Visit (Visit 1), Screening/Baseline assessment (Visit 2), 6-month Visits (Visits 3 and 4), 12-month Visits (Visits 5 and 6), and during the health coach phone calls.

In addition, 24-ambulatory blood pressure monitoring will be performed at each site with data downloaded via Spacelabs software and summary data transferred to REDCap. Data from these visits including participant

demographic information, vital signs, and other participant information will be uploaded into REDCap clinical research management software.

7.2.2 Case Report Forms

The study case report form (CRF) is a data reporting instrument for the study. All data requested on the CRF must be recorded. All missing data must be explained.

- All entries should be printed legibly in black ink.
- If any entry error has been made, to correct such an error, draw a single straight line through the incorrect entry and enter the correct data above it.
- All such changes must be initialed and dated.

NOTE:

- If a space on the CRF is left blank because the procedure was not done or the question was not asked, write "N/D".
- If the item is not applicable to the individual case, write "N/A".
- DO NOT ERASE OR WHITE OUT ERRORS.
- For clarification of illegible or uncertain entries, print the clarification above the item, then initial and date it.

7.3 Data Management

The Madison site, under the direction of MyHEART's lead statistician, will serve as the data coordinating center and the primary site to oversee timely and accurate data collection.

7.4 Data Monitoring

REDCap reports will be used to provide up-to-the-minute access to all entered data. This will allow verification of completeness, timeliness, reliability, and accuracy of collection and coding of data. Quality reports will also be sent to the MyHEART Steering Committee and will include comprehensive data on all quality control activities, including protocol adherence and violation, training, retraining, certification, and site visit reporting. The Steering Committee, along with the UW Biostatistics and Medical Informatics' lead MyHEART statistician, will develop and maintain standards to identify outlying values, and initiate and coordinate separate review of these observations for accuracy. Consistency checks and range checks have been built into the REDCap System.

7.5 Records Retention

For this non-FDA regulated study, all study data will be retained for at least 2 years after the last manuscript published under this clinical trials protocol number. If the analysis data will be retained beyond this window (example: for another study), a separate protocol and IRB approval will be obtained. The analysis data sets will only be shared with the Aurora Health Care research site as per the study structure outlined above. Any other outside institution will need to establish a data use agreement per UW Health's, University of Wisconsin School of Medicine & Public Health, and any other applicable party's protocol to acquire a copy of the de-identified dataset.

8 Assessment of Safety

Centralized safety oversight will be coordinated by the PI. The site PI will be notified of any adverse/serious adverse events for their specific site and will notify the PI, to ensure that all notifications (IRB, DSMB, etc.) occur according to protocol.

8.1 Specifications of Safety Parameters

8.1.1 Definition of Adverse Events (AE)

An *adverse event* (AE) is any symptom, sign, illness, or experience that develops or worsens in severity during the course of the study. Intercurrent illnesses or injuries should be regarded as adverse events. Abnormal results of diagnostic procedures are considered to be adverse events if the abnormality:

- results in study withdrawal
- is associated with a serious adverse event
- is associated with clinical signs or symptoms
- leads to additional treatment or to further diagnostic tests
- is considered by the investigator to be of clinical significance

8.1.2 Definition of Serious Adverse Events (SAE)

Adverse events are classified as serious or non-serious. A *serious adverse event* is any AE that fulfills at least one of the following criteria:

- is fatal
- is life-threatening
- requires or prolongs hospital stay
- results in persistent or significant disability or incapacity
- is a congenital anomaly or birth defect
- is an important medical event

Important medical events are those that may not be immediately life threatening, but are clearly of major clinical significance. They may jeopardize the subject, and may require intervention to prevent one of the other serious outcomes noted above. For example, treatment of bronchospasm in an emergency department would typically be considered serious. The primary pre-defined serious adverse events related to this study include hypoglycemia among patients with diabetes mellitus starting a new exercise program. All adverse events that do not meet any of the criteria for 'serious' should be regarded as *non-serious adverse events*. Throughout the study, any new clinically significant findings/abnormalities that meet the definition of an adverse event must also be recorded and documented as an adverse event.

Post-Study Adverse Event: All unresolved adverse events will be followed by the investigator until the events are resolved, the participant is lost to follow-up, or the adverse event is otherwise explained. At the last scheduled visit, the research visit investigator will instruct each participant to report any subsequent event(s) that the participant, or the participant's personal physician, believes might be related to participation in this study; the staff will contact the participant 30-days after study completion to inquire about any adverse events. The research visit investigator should notify the site-PI and the principal investigator (if different from the site-PI). The principal investigator will notify the study sponsor and IRB of any serious adverse event or death occurring up to 30 days after the participant has discontinued or terminated study participation that may be related to this study.

Hospitalization, Prolonged Hospitalization, or Surgery: Any adverse event that results in hospitalization or prolonged hospitalization will be documented and reported as a serious adverse event unless specifically instructed otherwise in this protocol. Any condition responsible for surgery should be documented as an adverse event if the condition meets the criteria for an adverse event.

Neither the condition, hospitalization, prolonged hospitalization, nor surgery are reported as an adverse event in the following circumstance:

- Hospitalization or prolonged hospitalization for diagnostic or elective surgical procedures for a preexisting condition. Surgery should **not** be reported as an outcome of an adverse event if the purpose of the surgery was elective or diagnostic and the outcome was uneventful.

8.1.3 Definition of Unanticipated Problems (UP)

OHRP considers unanticipated problems involving risks to participants or others to include, in general, any incident, experience, or outcome that meets all of the following criteria:

- Unexpected in terms of nature, severity, or frequency given (a) the research procedures that are described in the protocol-related documents, such as the IRB-approved research protocol and informed consent document; and (b) the characteristics of the participant population being studied;
- Related or possibly related to participation in the research (“possibly related” means there is a reasonable possibility that the incident, experience, or outcome may have been caused by the procedures involved in the research); and
- Suggests that the research places participants or others at a greater risk of harm (including physical, psychological, economic, or social harm) than was previously known or recognized.

This study will use the OHRP definition of UP.

Corrective actions or changes that will be considered in response to an UP will include:

- Modification of inclusion or exclusion criteria to mitigate the newly identified risks
- Implementation of additional safety monitoring procedures
- Suspension of enrollment of new participants or halting of study procedures for enrolled participants
- Modification of informed consent documents to include a description of newly recognized risks
- Provision of additional information about newly recognized risks to previously enrolled participants.

8.2 Classification of an Adverse Event

8.2.1 Severity of Event

The following guidelines will be used to describe severity:

Mild – Events require minimal or no treatment and do not interfere with the participant’s daily activities.

Moderate – Events result in a low level of inconvenience or concern with the therapeutic measures. Moderate events may cause some interference with functioning.

Severe – Events interrupt a participant’s usual daily activity and may require systemic drug therapy or other treatment. Severe events are usually potentially life threatening or incapacitating.

8.2.2 Expectedness

The principal investigator will be responsible for determining whether an AE is expected or unexpected. An AE will be considered unexpected if the nature, severity, or frequency of the event is not consistent with the risk information previously described for the study agent.

8.3 Time Period and Frequency for Event Assessment and Follow-Up

The occurrence of an AE or SAE may come to the attention of study personnel during study visits and interviews of a study participant presenting for medical care, or upon review by a study monitor. All AEs including local and systemic reactions not meeting the criteria for SAEs will be captured on the appropriate CRF. Information to be collected includes event description, time of onset, clinician’s assessment of severity, relationship to study product (assessed only by those with the training and authority to make a diagnosis), and time of resolution/stabilization of the event. All

AEs occurring while on study must be documented appropriately regardless of relationship. All AEs will be followed to adequate resolution.

Any medical condition that is present at the time that the participant is screened will be considered as baseline and not reported as an AE. However, if the study participant's condition deteriorates at any time during the study, it will be recorded as an AE. UPs will be recorded in the data collection system throughout the study.

Changes in the severity of an AE will be documented to allow an assessment of the duration of the event at each level of severity to be performed. AEs characterized as intermittent require documentation of onset and duration of each episode.

The PI will record all reportable events with start dates occurring any time after informed consent is obtained until 30 days (for non-serious AEs and SAEs) after the last day of study participation. At each study visit, the investigator will inquire about the occurrence of AE/SAEs since the last visit. Events will be followed for outcome information until resolution or stabilization. Breaches of confidentiality and emotional upset will be reported to the PI who will then review the incident with the study staff, information technology groups, and follow-up with the participant. The PI is responsible for making the reports to the DSBM, IRB and NHLBI.

8.4 Reporting procedures

This study will follow the HS-IRB reporting and submission timeframes:

<https://kb.wisc.edu/images/group78/18324/ReportingTimeframesJanuary2013.pdf>

Reporting time frames are in the Appendix.

This document will take priority for timeframes. The PI is responsible for reporting to the IRB, DSBM, and NIH.

8.4.1 Adverse Event (AE) Reporting

Adverse events must be reported once the participant undergoes any study procedures and adverse events must be reported during the entire active study period and for 30 days following the last administration of study treatment. The IRB, DSBM and NHLBI will be notifications about AEs.

8.4.2 Serious Adverse Event (SAE) Reporting

The study clinician will complete a SAE Form within the following timelines:

All deaths and immediately life-threatening events, whether related or unrelated, will be recorded on the SAE Form and submitted to the DCC/study sponsor within 24 hours of site awareness. See **Section 1, Key Roles** for contact information. Other SAEs, regardless of relationship, will be submitted to the DCC/study sponsor within 72 hours of site awareness.

All SAEs will be followed until satisfactory resolution or until the site investigator deems the event to be chronic or the adherence to be stable. Other supporting documentation of the event may be requested by the DCC/study sponsor and should be provided as soon as possible.

8.4.3 Unanticipated Problem (UP) Reporting

The site investigator will be responsible for creating and completing a UP report form. Incidents that meet the OHRP criteria for UPs will be reported promptly per the HS IRB timeline (see Appendix).

- All UPs should be reported to appropriate institutional officials as required by the HS-IRB, the NHLBI, DSBM, and OHRP upon receipt of the report of the problem from the investigator per the HS IRB policy:
<https://kb.wisc.edu/images/group78/18324/ReportingTimeframesJanuary2013.pdf>

The UP report will include the following information:

- Protocol identifying information: protocol title and number, PI's name, and the IRB project number;
- A detailed description of the event, incident, experience, or outcome;
- An explanation of the basis for determining that the event, incident, experience, or outcome represents an UP;
- A description of any changes to the protocol or other corrective actions that have been taken or are proposed in response to the UP.

8.4.4 Reporting of Pregnancy

Subjects will also be immediately withdrawn from the study if they report being pregnant or planning to become pregnant. Study data acquired up to the withdrawal date will be analyzed. No additional routine pregnancy reporting is indicated for this study.

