2.1 Background and Rationale

Uncontrolled hypertension in young adults is an enormous public health burden.^{1,2} In the U.S., over 10 million 18-39 year-olds (1 in 5 men; 1 in 6 women) have hypertension,³⁻⁶ increasing their risk of heart failure, stroke, and chronic kidney disease.^{5,7-10} The medical costs of hypertension and its complications are \$131 billion/year,^{11,12} contributing to 1,000 deaths per day.^{3,5,11,13-15} Young adults with hypertension have a higher lifetime risk for cardiovascular disease, especially with complicated hypertension (hypertension with diabetes or chronic kidney disease).^{9,14-20} Hypertension control reduces morbidity, mortality, and future healthcare costs,²¹⁻²⁵ yet, only 35% of young adults with hypertension in the U.S. have achieved blood pressure control (blood pressure <140/90 mmHg).²⁶⁻²⁹

While hypertension self-management programs targeted towards adults ≥ 50 years old reduce blood pressure,³⁰⁻⁴⁸ they primarily focus on medication titration.⁴⁹ In contrast, a trial of lifestyle modifications is commonly the initial hypertension treatment step, rather than a medication, among young adults.⁵⁰ Medication initiation is also not enough to achieve long-term blood pressure control in young adults. Even with medication adherence, systolic blood pressure continues to increase from younger to older age.⁵¹ Therefore, young adults need additional hypertension self-management (home blood pressure monitoring and lifestyle modifications) to lower blood pressures and reduce the amount of medication they may need over a lifetime.⁵²⁻⁵⁵

The Institute of Medicine⁵⁶ highlighted the importance of self-management support to learn and effectively perform self-management.^{30,34,36,57,58} In multiple studies among older adults, hypertension self-management is superior to office-based management.^{30,34,36,57-59} However, in contrast to older adults, young adulthood is a time of frequent healthcare and vocational transitions, new life responsibilities, and less interest in health-related goals (*i.e.*, prevention of heart attack and stroke).^{60,61} Thus, the content and method of delivery of hypertension self-management must be individualized to young adults and address barriers specific to this population.⁶²⁻⁶⁴

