Adverse Event Reporting Period: Adverse events must be reported once the subject undergoes any study procedures, and adverse events must be reported during the entire active study period and for 30 days following the last administration of study treatment.

Withdrawal of subjects: Any subject who experiences an adverse event or serious adverse event will be immediately withdrawn from the study. All subjects have the option to withdraw from the study at any time. Subjects will also be immediately withdrawn from the study if they report being pregnant, planning to become pregnant, or develop a medical condition (even if unrelated from this study) that prevents them from ongoing participation in the study.

Post-study Adverse Event: All unresolved adverse events will be followed by the investigator until the events are resolved, the subject is lost to follow-up, or the adverse event is otherwise explained. At the last scheduled visit, the investigator will instruct each subject to report any subsequent event(s) that the subject, or the subject's personal physician, believes might be related to participation in this study. The investigator should notify the study sponsor, DMC, and IRB of any serious adverse event or death occurring up to 30 days after the subject has discontinued or terminated study participation that may be related to this study.

Hospitalization, Prolonged Hospitalization, or Surgery: Any adverse event that results in hospitalization or prolonged hospitalization will be documented and reported as a serious adverse event unless specifically instructed otherwise in this protocol. Any condition responsible for surgery should be documented as an adverse event if the condition meets the criteria for an adverse event.

Neither the condition, hospitalization, prolonged hospitalization, nor surgery are reported as an adverse event in the following circumstance: Hospitalization or prolonged hospitalization for diagnostic or elective surgical procedures for a preexisting condition. Surgery should **not** be reported as an outcome of an adverse event if the purpose of the surgery was elective or diagnostic and the outcome was uneventful.

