4.1 Subject Population

The age range of the subjects is 18-39 years. The young adult age range is based upon the hypertension guidelines for children and adolescents which applies to <18 year-olds.¹²⁵ The National Health and Nutrition Examination Survey (NHANES) data (as reported by the American Heart Association⁶⁷ and the Center for Disease Control³) limits young adults to <40 years old. Young adults were selected for this research since they have the lowest hypertension control rates compared to middle aged and older adults and lack effective hypertension interventions.

There are no enrollment restrictions based upon race or ethnic origins. We will target recruitment by minority status to ensure that we achieve our expected enrollment numbers. Nationally, the prevalence of hypertension among young adults is greater in young males and Blacks. We expect a higher recruitment of minority patients from an IRB-approved urban site based on the racial/ethnic distribution of patients. Women who are or become pregnant will be excluded to ensure we do not include patients with pregnancy-induced hypertension.

The information provided in the Targeted/Planned Enrollment Table represents the gender, ethnic, and racial make-up from a sample of potentially eligible subjects in the electronic health record:

UW Health: Sex: 62% male; Ethnicity: 5% Hispanic/Latino; the racial make-up is 82% white, 13% black, 2% Asian, 0.3% American Indian or Alaska Native, and 3% “more than one race”.

4.2 **Inclusion Criteria**

Inclusion Criteria
1. Willing and capable of giving written informed consent
2. Willing to comply with all study procedures and be available for the duration of the study
3. Males and females ages 18-39 years old at the start of the study (inclusive)
4. A single ICD-10 diagnosis code R03.0 (elevated blood pressure reading, without diagnosis of hypertension) in the last 24 months, OR, a minimum of two hypertension ICD-10 coded visits with a provider (MD, DO, PA, NP) on different dates in the last 24 months, with at least one code in the past 18 months
5. Medically home at UW Health or Aurora Health Care

The inclusion criteria are designed to ensure that patients who have a single visit to a clinic but seek primary care permanently elsewhere are not included in our study.¹²⁶ The patient has to be managed at the same healthcare system prior to and during the study.

4.3 **Exclusion Criteria**

Exclusion Criteria

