4.7.2 When and How to Withdraw Subjects

Participants will be educated on the consent form that they are able to withdraw at any time without adverse effects to receiving healthcare services.

Women that are currently pregnant or plan to become pregnant during enrollment screening will be excluded from study participation. If a participant becomes pregnant during the study, she is excluded immediately from further participation in all study activities. The presence/absence of birth control is not an inclusion or exclusion criteria. Pregnancy testing is not part of the study protocol. Once enrolled in the study, individuals in either the usual care or intervention group who become ineligible during the study (e.g., self-report of a new condition in the list of exclusion criteria) will be informed that their participation has ended and will be provided the reason for ending their study participation.

No medications will be administered by the study staff. Procedures are not needed to transition subjects of study agents or alternate therapy if withdrawn from this study.

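### Two sections withdraw a participant who only reports planning a pregnancy; the withdrawal section does not clearly say so, no reason is given, and later blood pressures are lost although obtainable

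*Combined protocol and SAP*

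**What the plan says.** Two sections withdraw a participant on a stated plan alone. Section 8.4.4 says: "Subjects will also be immediately withdrawn from the study if they report being pregnant or planning to become pregnant". Section 2.5.4 says the same and adds medical conditions: "Subjects will also be immediately withdrawn from the study if they report being pregnant, planning to become pregnant, or develop a medical condition".

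Section 4.7.2 is worded differently. It ties planning to entry: "Women that are currently pregnant or plan to become pregnant during enrollment screening will be excluded from study participation". For the period after enrolment it names pregnancy only: "If a participant becomes pregnant during the study, she is excluded immediately from further participation in all study activities". It also ends participation for people in either arm "who become ineligible during the study (e.g., self-report of a new condition in the list of exclusion criteria"). Exclusion 13 in section 4.3 covers being pregnant or planning a pregnancy within 12 months.

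Section 4.1 gives one reason: "Women who are or become pregnant will be excluded to ensure we do not include patients with pregnancy-induced hypertension". Section 4.5 adds that antihypertensive medication is managed differently in pregnant women, and that new exercise or diet changes may carry more risk than benefit for some of them. Section 2.5.1 expects no reproductive risk from the trial.

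On data, 8.4.4 says that what was collected up to withdrawal will be analysed. Section 4.7.3 says withdrawn participants are analysed by intention to treat, with multiple imputation and sensitivity analyses. It schedules no measurements after withdrawal.

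**The concern.** A participant who says she plans a pregnancy is not pregnant, may still consent, and can still attend the research clinic. Under 2.5.4 and 8.4.4 she leaves the study at once. Her remaining blood pressures, which are the co-primary outcome, are then imputed when they could have been measured. In the usual care arm there is not even any coaching to stop.

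Two things are at stake. The first is avoidable missing outcome data in a trial analysed by intention to treat. The second is possible imbalance. The trigger is a self-report, and the arms do not have the same number of contacts in which to make one. If plans come to light earlier or more often in the coached arm, more of its participants would be removed before the 6-month measurement. The withdrawal rate and reasons, a safety endpoint in 3.1.3, would carry the same distortion.

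**Working it through.** **1. The rules side by side.**

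| Section | Pregnant on study | Plan reported on study |
|---|---|---|
| 2.5.4 | withdrawn | withdrawn |
| 8.4.4 | withdrawn | withdrawn |
| 4.7.2, pregnancy sentences | participation ends | not named; planning is tied to screening |
| 4.7.2, general clause | reached through exclusion 13 | possibly reached through exclusion 13; the example given is a new condition |

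The difference is an omission and an ambiguity in 4.7.2. It is not a pair of opposite rules.

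**2. The reasons.** Pregnancy-induced hypertension (4.1), medication management (4.5) and exercise or diet risk (4.5) all apply to a pregnant woman. None is stated for a woman who only has a plan, and none is a reason against measuring her blood pressure.

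**3. What is lost.** Only measurements due after the withdrawal date. A participant withdrawn before Visit 3 loses the 6- and 12-month values. One withdrawn after the 6-month visits keeps the 6-month value and loses the 12-month one.

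**4. Occasions to disclose before Visit 3.** Section 5.4.2 gives the intervention arm 12 coach calls, one every two weeks. The visit-window table in 5.4.3 names a scheduler call for usual care. Section 9.4 mentions phone surveys in both arms, and the study calendar is in an appendix that is not available here, so the full contact schedule cannot be compared.

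**5. Size.** The inputs from the documents are:
- 340 randomised (6.1);
- 62% male in the UW Health sample (4.1), so 38% women, assumed to hold at both sites;
- effective sample size 264, or 132 per arm (6.1);
- differences of 6.3 and 4.0 mmHg, with SDs of 13.6 and 9.7 (6.1);
- two-sided alpha of 0.025 for each outcome (6.1).

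The documents give no rate of reported plans. I assume 3-10% of women over 12 months.

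- Women: 0.38 × 340 = 129.
- Affected: 0.03 × 129 = 4 to 0.10 × 129 = 13, which is 1.1% to 3.8% of 340.

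The plan's own power comes first, from power = Φ(d / (SD × √(2/n)) − 2.241):
- Systolic: 6.3 / (13.6 × √(2/132)) = 3.763; Φ(3.763 − 2.241) = 0.936 (stated 0.94).
- Diastolic: 4.0 / (9.7 × √(2/132)) = 3.350; Φ(3.350 − 2.241) = 0.866 (stated 0.87).

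Both stated figures are reproduced. The next step removes further participants, taking each as lost at 6 months and not already counted in the planned dropout:

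| Extra loss, share of 340 | People | N left | Power, systolic | Power, diastolic |
|---|---|---|---|---|
| 0% | 0 | 264 | 0.936 | 0.866 |
| 2% | 7 | 257 | 0.930 | 0.857 |
| 5% | 17 | 247 | 0.919 | 0.841 |

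The assumed 4-13 people are fewer than the 17 in the last row, so the power cost is below about 2 points (systolic) and 3 points (diastolic). Starting instead from 340 × 0.85 = 289, a 5% extra loss moves power from 0.955/0.897 to 0.943/0.877. The gap between 289 and the plan's 264 is a separate matter and does not affect this point.

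**The case against.** The case against is substantial, and much of it stands.

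- **The sections do not flatly contradict each other.** 2.5.4 and 8.4.4 agree, and the general clause in 4.7.2 may cover planning. This stands: the fault is unclear wording. It does not supply a reason for stopping measurement.
- **Exclusion 13 already removes women with plans at entry.** This stands. Only changed plans remain, so the numbers are small, and some may sit within the planned dropout.
- **Different medication management in pregnancy bears on blood pressure in both arms.** True, but it concerns pregnancy, not a plan.
- **Unequal detection is not shown.** This stands. No listed coaching module asks about pregnancy plans, and the calls end at 6 months, so they cannot reveal plans formed later. The mechanism is plausible, with no demonstrated size or direction of bias.

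A reader might also infer two stronger points that the documents do not support.

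The first is that 8.4.4 and 4.7.3 conflict over data. Analysing what was observed and imputing the rest are compatible; 8.4.4 merely does not mention imputation.

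The second is that changing health system also ends follow-up. Section 4.2 says: "The patient has to be managed at the same healthcare system prior to and during the study", and section 2.1 notes that "young adulthood is a time of frequent healthcare and vocational transitions". But no withdrawal text names a change of system. The example in 4.7.2 is an exclusion-list condition, whereas medical home is an inclusion criterion, and the purpose stated in 4.2 is to keep out single-visit patients at entry. Withdrawal for this cause is an inference and not a rule of the plan.

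**Conclusion.** The point holds in a limited form. As written, 2.5.4 and 8.4.4 end participation for a non-pregnant, consenting participant on a stated plan; 4.7.2 leaves the matter unclear; no section gives a reason that fits; and 4.7.3 replaces obtainable co-primary pressures with imputed ones. On the assumed 3-10% of about 129 women, this touches 4-13 participants, and the effect on power is minor. The argument therefore rests on avoidable missing outcome data, with arm imbalance as a possibility. It depends on the assumed rate, on the UW Health sex ratio applying at both sites, and on withdrawal meaning no further visits, which is the only reading that the text provides for. It is a cheap improvement and not a threat to the trial's main conclusion.

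**What to change.** Reconcile 2.5.4, 4.7.2 and 8.4.4 so that one statement says which events end participation. What happens to coaching after a reported plan is for the investigators to decide, and nothing here proposes a clinical rule.

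Separately, state in 4.7.3 that for participants who are not pregnant and still consent, any decision to end coaching does not end outcome measurement at the remaining scheduled visits, in either arm. Add to 8.4.4 that the missing-data approach of 4.7.3 applies; this is a clarification. Optionally, clarify in 4.2 that the requirement to stay in the same health system is not a withdrawal trigger.

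The cost is amended protocol and consent wording, plus follow-up visits for a few participants no longer coached. Visits 3-6 are already planned for both arms, so no new procedure is needed.
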